5.0 TISSUE BIOPSY AND SURGICAL PLACEMENT OF IMPLANTS

5.1 Cone Beam CT Imagery

A Cone Beam Computed Tomography (CBCT) scan will be made eight weeks after the extractions, prior to any manipulation of tissue at the study sites. The images will be used to obtain a 3-dimensional database of the participant's anatomy from the volumetric tomography. Axial, sagittal, and cross-images will be reconstructed to measure tooth socket volume.

5.2 Surgical Implant Placement

The implants utilized are identical with the exception of the collar surface characteristics (Table 4). Each patient will receive either implants with an LTT or an RBT surface according the study randomization schedule.

5.3 Patient Preparation

Prior to implant surgery the subjects will be given a loading dose of antibiotics based on their medical history and concomitant medications. Local anesthesia will be achieved in the region by regional block or local infiltration. Conscious sedation may be added at the surgeon's discretion to help manage a patient's anxiety. The facial area will be scrubbed and the oral cavity disinfected by rinsing for 1 minute with a (0.12% chlorhexidine gluconate) antimicrobial oral rinse prior to the procedure.

Once the treatment areas are sufficiently anesthetized a crestal incision will be made and full-thickness flaps will be raised. With the aid of a surgical guide, the proposed implant sites will be identified; measurements of the alveolar ridge will be captured, using a UNC-15 periodontal probe and recorded on the implant surgery CRF.

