1.0 BACKGROUND AND SIGNIFICANCE

1.1 Tooth Extraction Socket Preservation

Tooth extraction is often associated with resorption of alveolar ridge height and width and with compromised soft tissue contours¹⁻⁸. An increasingly common periodontal practice combines skilled surgical technique with extraction site grafting. These procedures are thought to retard resorption of the socket volume while lending some control over bone-fill – thereby preserving the integrity of the alveolar ridge for future reconstruction with dental implants.

Limited evidence-based data exists to support a variety of bone grafting materials used to prevent the resorption of bone in the extraction socket. Autografts, allografts, xenografts and alloplasts are all considered viable options to maintain and regenerate the site^{1-6, 8}.

Artzi et al.⁴ evaluated the histology and histomorphometric analyses of 15 extraction sockets in 15 patients treated with cancellous porous bovine bone mineral. All procedures involved extraction sockets of anterior teeth and premolars; primary closure of the extraction sockets was achieved with a pediculated split palatal flap. The bone fill of the extraction sockets was 82.3% lamellar type bone, located in the apical portion of the sockets, and the woven type of bone found in the coronal part of the sockets. The investigators concluded that the cancellous porous bovine bone mineral was present 9 months after the procedure and that resorbability of the bone graft material needed further assessment. In a second phase of the same study, Artzi et al.⁵, investigated the grafted extraction sockets by means of histochemical analysis and demonstrated the biocompatibility of the cancellous bovine bone mineral.

In another study, Froum et al.⁶ grafted 30 extraction sockets and divided them into three different groups. Bioactive glass and demineralized freeze-dried bone allograft (DFDBA) were used in the two test groups; the control group received no material at all. Flaps were coronally positioned to achieve closure of the site by primary intention. The bioactive glass group exhibited 59.5% of vital bone outperforming the DFDBA and non-grafted extraction socket groups that presented 34.7% vital bone formation 6 to 8 months following the surgical procedure. The difference in vital bone was not considered statistically significant among the three groups.

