2.3 Hypotheses and Specific Aims

Hypothesis I

Bone grafted sites preserve alveolar ridge dimensions of extraction sockets more effectively than extraction sites that have healed without grafting.

Specific Aims

- 1: Compare alveolar ridge dimensions in grafted extraction sockets to that of sites healed without grafts after 8 weeks of post-extraction healing.

Hypothesis II

The addition of growth factors to bone grafting materials will enhance osseous and soft-tissue healing.

Specific Aims

- 2: Assess the efficacy of bone grafting with and without enrichment with growth factors to preserve the volume of bone in extraction sockets.

- 3: Compare soft tissue healing between groups at week-1, week-2, week-4 and after 8 weeks of post-extraction healing

- 4: Assess quantitative bone fill across groups after 2 months of post-extraction healing
- 5: Compare qualitative bone fill across groups after 2 months of post-extraction healing.
- 6: Assess and compare the relationship of osseous healing and implant stability at insertion across groups after 2 months of post-extraction healing.

Hypothesis III

Laser Thread Textured (LTT) dental implant will help preserve longitudinal peri-implant crestal bone more effectively than implants with Resorbable Blast Texturing (RBT).

Specific Aims

- 7: Assess the efficacy of LTT and RBT surface topographies when surgically implanted into extraction sockets.
- 8: Assess peri-implant soft-tissue healing adjacent to LTT and RBT surfaced implants.
- 9: Assess changes in longitudinal crestal bone level across extraction groups and between implant groups at 12 and 24 months after surgical implant placement.

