4.6 Surgical Extractions

All surgeries will be performed by qualified clinicians in an appropriately equipped surgical operatory located in the Periodontal Clinic at UAB School of Dentistry.

Prior to extraction surgery, participants will be given a loading dose of antibiotics based on their medical history and concomitant medications. A suggested prophylactic regimen follows:

2 gm of Amoxicillin 1 hour prior to the procedure followed by 500mg (TID) for 7 days

Patients with reported allergy to Amoxicillin:

600mg Clindamycin 1 hour prior to the procedure followed by 300mg (TID) for 7 days

The facial area will be scrubbed and the oral cavity disinfected by rinsing for 1 minute with a (0.12% chlorhexidine gluconate) antimicrobial oral rinse. Prior to extractions clinical photographs will be taken from the buccal and occlusal aspects. Photographs will be taken in a 1:1 ratio using a Nikon D-70 camera with a sunpack ringflash.

After preparation and isolation of the surgical area, anesthesia will be achieved in the region by regional block or local infiltration. Conscious sedation may be added at the surgeon's discretion to help manage patient anxiety.

The teeth will be extracted as atraumatically as possible, without raising a flap, utilizing periotomes and the Easy Extrac system. Grafting procedures will include the use of FDBA and collagen plugs in all experimental groups. In all groups, the integrity of the remaining socket walls will be assessed and measurements recorded on the surgical CRF. The sockets will be debrided and a bleeding surface created by decorticating the socket walls with either a curette or a surgical round burr.

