4.8 Surgical Extraction Data Collection

The following data points will be collected and recorded on the surgical CRF: A description of the integrity of each of the socket walls will be recorded as follows.

4.8-1 Measurements of the Mesio-distal distance and the buco-lingual distance of the socket walls

4.8-2 Measurements of dehiscence and fenestration defects made with a UNC-15 periodontal probe in relation to the adjacent socket crest and rounded up to the nearest millimeter.

4.8-3 Wound Measurements – Mesio-distal distance and bucco-lingual distance of the soft tissue wound margins after suturing made with a UNC-15 periodontal probe and rounded to the nearest millimeter.

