8.0 RADIOGRAPHIC AND PHOTOGRAPHIC SURVEYS

8.1 Cone Beam Computed Tomography

Cone beam computed tomography (CBCT) images will be used to obtain a 3-dimensional database of the patient's anatomy from the volumetric tomography. Axial, sagittal, and cross-images will be reconstructed to measure the tooth socket volume. Hounsfield units will be calculated to assess the relative tissue density for each study site. CBCT scans will be obtained after the completion of the extraction and grafting procedures and again at 8 weeks after the extractions.

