12.4 Statistical Analysis

The general approach to statistical analysis of the study aims will be based on mixed-model analysis of variance (ANOVA). This approach will accommodate the inclusion of correlated observations due to study subjects potentially contributing measurements of more than one single tooth site to the analysis.

The sample distributions will be examined for each outcome variable. If these distributions depart substantially from normality, transformations of the data will be evaluated. If normality cannot be established by transformation, rank-based analyses will be used.

Subjects will be included as a random effect on the analyses that include multiple observations per subject. For analysis of histological data, only one tooth site per subject will be evaluated and the model will not include a random effect.

Smoking status will be included in all models in order to account for differences in response between smokers and non-smokers, and so that the analysis will correspond to the study's randomization strategy. Comparisons between smokers and non-smokers are not a primary interest in the study.

For aims in which interaction terms are of interest, significant interaction terms will be investigated using plots of least square means and separate post-hoc analyses for individual time points.

Hypothesis 1

Differences among the four groups will be evaluated by the overall F-test for the ANOVA. Pairwise comparisons among group means will be conducted using Tukey's test. Contrasts will be constructed to address each specific aim (SA).

SA-1: Compare alveolar ridge dimensions in grafted extraction sockets to that of sites healed without grafts after 8 weeks of post-extraction healing.

This SA will be addressed by comparing the combined mean of the three graft groups (FDBA/TCP, DDBA/TCP/PRP, FDBA/TCP/PDGF) with that of the CONTROL group by calculating a contrast and the corresponding F-test. Pairwise comparisons among means will be conducted using Tukey's test..

Hypothesis II

The addition of growth factors to bone grafting materials will enhance osseous and soft tissue healing.

SA-2: Assess the efficacy of bone grafting with and without enrichment with growth factors to preserve the volume of bone in extraction sockets.

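### SA-1, the only aim under Hypothesis I, is a week-8-only contrast of an undefined ridge measurement; reading ridge width and height on the two planned CBCT scans, with baseline adjustment, would define and sharpen it

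*Combined protocol and SAP*

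**What the plan says.** Section 2.3 states Hypothesis I in comparative form: "Bone grafted sites preserve alveolar ridge dimensions of extraction sockets more effectively than extraction sites that have healed without grafting". The background (1.1) gives the clinical reason: "Tooth extraction is often associated with resorption of alveolar ridge height and width". One aim, SA-1, sits under this hypothesis. Section 12.4 words it as: "Compare alveolar ridge dimensions in grafted extraction sockets to that of sites healed without grafts after 8 weeks of post-extraction healing".

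The analysis in 12.4 consists of "comparing the combined mean of the three graft groups" with the control mean, by a contrast and F-test, plus Tukey pairwise comparisons. Smoking status is in every model, and subject is a random effect where there are several sites. SA-1 names no baseline value, change score, instrument or dimension.

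The possible sources of a ridge measurement are:

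- **Week 8, probe (5.3).** After full-thickness flaps are raised, "measurements of the alveolar ridge will be captured, using a UNC-15 periodontal probe and recorded on the implant surgery CRF". The dimension, landmark and reference point are not stated.
- **Extraction, probe and direct readings (4.8).** "Measurements of the Mesio-distal distance and the buco-lingual distance of the socket walls", together with dehiscence and fenestration defects and the soft-tissue wound margins. None is labelled a ridge measurement. Access also differs from week 8 (4.6): "The teeth will be extracted as atraumatically as possible, without raising a flap".
- **CBCT at V-2 and week 8 (5.1, 8.1).** "Axial, sagittal, and cross-images will be reconstructed to measure the tooth socket volume", with Hounsfield units for relative density. Section 12.1 adds quantitative bone fill. Neither ridge width nor ridge height is named.

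**The concern.** The hypothesis is about preservation, yet its one aim uses a single time point and does not say what is measured. Three things follow.

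1. Eligible sites run from maxillary anterior teeth to premolars in both jaws, so original ridge size will differ between sites. The SA-1 model has no term for baseline size or tooth type, so this variation goes into the error. The plan's own power for a medium effect is already only about 57%.
2. Without a baseline reading of the same dimension, the trial can say that one arm's ridges are larger than the other's at week 8. It cannot say how much ridge either arm lost.
3. Probe or CBCT, width or height, week-8 value or change could all be chosen after the data are seen. Height, half of the stated rationale, might not be reported at all.

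The scans that would settle this are already scheduled at both times.

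**Working it through.** **Inputs from the plan (12.5).** Effective sample sizes 25 (control) and 75 (grafted); difference 0.50 sd; two-sided 5% level; stated power about 57%; stated difference detectable with 80% power about 0.65 sd.

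**Step 1: reproduce the plan's figure.** Two-sample t-test, df = 25 + 75 − 2 = 98.

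- Standard error in sd units: √(1/25 + 1/75) = √0.05333 = 0.2309.
- Noncentrality: 0.50 / 0.2309 = 2.165.
- Power from the noncentral t: 57.3% (normal approximation 58.1%).
- Detectable difference at 80% power: 0.653 sd (normal approximation 0.647).

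Both stated figures reproduce. The calculation uses no baseline information, which matches SA-1 as written.

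**Step 2: add a baseline covariate.** Let r be the within-group correlation between the baseline and week-8 readings of the same dimension. The documents give no value, so r is an assumption. Adjustment multiplies the residual variance by 1 − r², so the standardized difference becomes 0.50/√(1 − r²). An unadjusted change score has variance 2(1 − r), giving 0.50/√(2(1 − r)). The detectable difference with the covariate is 0.653 × √(1 − r²). The 98 df are kept; the one df spent on the covariate is ignored.

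| Assumed r | Week 8 only | Change score | Covariate-adjusted | Standardized difference, adjusted | Detectable at 80% power, adjusted |
|---|---|---|---|---|---|
| 0.3 | 57% | 44% | 61% | 0.524 | 0.62 sd |
| 0.5 | 57% | 57% | 70% | 0.577 | 0.57 sd |
| 0.7 | 57% | 79% | 85% | 0.700 | 0.47 sd |

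The covariate form is better than the week-8-only analysis at each of these correlations. The change score is worse than week 8 only when r is below 0.5, so adjustment is the form to specify.

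**Step 3: is a usable baseline available?** Section 8.1 places the first CBCT after extraction and grafting are complete, and 4.7 agrees. A V-2 reading is therefore taken after treatment. Graft is packed inside the socket and no flap is raised, so points on the outer cortex and on fixed anatomy should be little affected where walls are intact. Where walls are deficient, which 4.8-2 provides for, graft could change the apparent contour. The 4.8-1 socket-wall distances are a further baseline recorded at the extraction surgery. They cover the horizontal directions only and describe the socket, so they can serve as a covariate but not as the same measurement.

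**The case against.** The strongest reply is that nothing here stops the trial from testing its hypothesis. A reader might infer that SA-1 cannot show preservation without a baseline. The documents do not support that: Hypothesis I is comparative, participants are randomized to the four extraction groups (4.2), and original ridge size is then noise rather than bias. A week-8 difference is valid evidence that grafting preserves more. This objection stands and limits the point to definition, precision and within-arm loss.

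Other replies also have force:

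- **Height is not excluded.** Section 5.3 speaks of measurements in the plural and leaves the dimension open. Hypothesis I and SA-1 say only dimensions; height and width come from the rationale. A Manual of Procedures is listed as Appendix E and was not available for this review, so it or the CRF may hold the definitions. Even so, the SAP should name the SA-1 variable.
- **No invalid subtraction is planned.** A reader might suppose that socket-wall distances at extraction will be subtracted from the week-8 ridge reading. No section says so.
- **Rounding.** Whole-millimetre recording is stated for defects and wound margins (4.8-2, 4.8-3), not for the ridge reading, so no power loss from rounding can be claimed.
- **The scans have wider uses.** The synopsis lists radiographic change in osseous architecture over time as an outcome, and SA-2 compares bone volume across all four groups, control included. This shows intent to measure change but still defines neither ridge width nor height.
- **The V-2 scan follows grafting.** Adjusting for a value that treatment has altered could remove part of the effect. This calls for a safeguard, given in the fix; it does not defeat the proposal.

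**Conclusion.** The point holds as an endpoint-definition and efficiency gap that should be closed. SA-1 has no named dimension, landmark, instrument or baseline; ridge height is named as a measurement nowhere; and the two CBCT scans are not assigned to ridge dimensions. The comparison between arms remains valid.

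The size of the gain depends on r, which is assumed. Power at 0.50 sd moves from 57% to 61%, 70% or 85% at r of 0.3, 0.5 or 0.7, so it passes 80% only at the top of that range. These figures take the plan's effective sample sizes as given, apply to one dimension at a time, and hold only if treatment does not affect the covariate. No figure stated in 12.5 for SA-1 is disputed.

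**What to change.** - **5.1 and 8.1:** define bucco-lingual ridge width at a fixed depth below a stable landmark, and ridge height to that landmark. Read both on the V-2 and week-8 CBCT scans after registration.
- **12.4, SA-1:** make the week-8 CBCT readings the outcomes, each adjusted for the baseline reading of the same dimension. State which of the two leads, or how they are tested together. Report change from baseline by arm descriptively. Keep the flap-open probe reading as supportive, with its dimension and landmark stated.
- **Safeguard for the post-graft scan:** take the baseline from outer cortical and landmark-based points that graft inside the socket does not alter. Run a sensitivity analysis with the 4.8-1 socket-wall distances as the covariate instead; it bears most directly on width.

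The cost is two extra readings per site on each of two scans already taken, plus protocol and SAP wording. There is no new scan, visit or procedure. The remaining downside is possible graft influence on the V-2 reading where socket walls are deficient, which the sensitivity analysis is meant to expose.

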5.4 Implant Selection

The diameter and length of the implant will be determined by the surgeon based on the tooth location, anatomy, and bone volume determined from the CT scan prior to placement. The collar surface will be determined by the randomization scheme.

Table 4 Implant characteristics

Implant Material:	Titanium Alloy - Ti-6Al-4V
Collar Surfaces:	Resorbable Blast Texturing (RBT) or Laser Thread Texturing (LTT)
Connection:	1.5mm deep internal hexagon
Diameters:	Ø3.5mm Ø4.0mm Ø5.0mm Ø6.0mm
Lengths:	9mm, 10.5mm, 12mm and 15mm

5.5 Drilling & Biopsy Technique

A standard drilling technique will be utilized except for a modification in the depth of the osteotomy and biopsy obtained from study sites described below. Copious amounts of sterile irrigant will be used in the osseous drilling procedure to prevent heating and thermal necrosis of the bone and surrounding tissue. The drill speed may be adjusted up to a maximum of 2500 rpm during the procedure. Thread forming or taping may be indicated in very dense bone and should be at a maximum of 30 rpm.

The surgeon will start with the 2mm diameter trephine drill for study sites and then proceed to increase the width with progressive depth drill depending on the implant diameter to be used at the site. The trephine with bone contained within will be harvested from the center core of one study site, per patient and will be immediately placed in fixative for later histological analysis. Vials will be labeled with the participant's ID and the date of biopsy; laboratory technicians will be blinded to knowledge of participant group assignment.

In this protocol the implant collars are to be positioned 1mm above the level of the crestal bone. This is accomplished by adjusting the depth of the osteotomy for each implant by 1mm. For example the

osteotomy depth for a 15 mm length implant should be 14mm. Since the collars of the implants are 1 mm above the bone crestal bone drills will not be used in this protocol.

5.6 Implant Placement

The sterile blister pack containing the implant will drop onto a sterile field and after thorough irrigation of the site the implant will be inserted directly into the prepared bone site. After placement with the collar 1mm above the bone the insertion torque will be measured with a torque wrench and recorded on the case report forms. A cover cap will be placed on the implant and the surgical wound sutured.

5.7 Immediate Post-Operative Procedures

Standardized intra-oral periapical dental radiographs will be made of each study site. Written and verbal post-operative instruction will be provided to each participant. An antimicrobial mouth rinse and ice packs will be dispensed. Antibiotics will be prescribed for 7 days; analgesics will be prescribed on an as needed basis at the discretion of the surgeon.

6.0 RESTORATION OF IMPLANTS

6.1 Implants Uncovered

Implants will be uncovered upon the investigator's determination that the implants are sufficiently integrated to withstand the forces of loading. In general, mandibular implants will be uncovered and restoration initiated approximately 4 months after placement; maxillary implants will be uncovered and restoration initiated approximately 6 months after placement. When the implants are uncovered, clinical photographs will be taken before, during and after the procedure; following the procedure, standardized intra-oral radiographs of each implant site will be made.

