6.2 Placement of the final restoration

Each implant will be restored in the conventional manner with an aesthetically pleasing single crown restoration. Restoring materials will be selected by the restoring dentist based on discretion of the dentist and individual patient needs. Prosthetic restoration of the implants will require numerous visits to the restorative dentist over a period of one to two-months. The restoring dentist will advise when additional visits are necessary. Photographs will document each step in the restoration process and of radiographs be taken of each area when the final restoration is cemented.

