7.0 LONGITUDINAL FOLLOW-UP

7.1 Post-Restoration Follow-up Evaluations (12-months and 24-months after implant placement)

Participants will return to the clinic at 12 and 24 months following implant placement. Evaluation of implant function and surrounding tissue health will be determined based on an interview with the participant, clinical examination of the study sites and an analysis of radiographic and photographic data.

At each visit, study personnel will review and update the participant's health history and record any adverse experiences; a study dentist will complete a thorough periodontal evaluation of the implant area and provide an assessment of the prosthetic attachment interface. A set of standardized periapical radiographs and clinical photographs will be made.

Case report forms will be used to record the following observations for each implant site:

- Overall soft tissue health
- Plaque and gingivitis scores (modified Löe and Sillness)
- Pocket depth and clinical attachment level
- Implant Stability
- Retention and stability of prosthetic attachment
- Overall aesthetics (soft tissue contours)
- Assessment of reported pain
- Implant survival

Each participant will complete a patient satisfaction questionnaire. Participants will be asked to report their own assessments for the following criteria:

- Comfort
- Speech
- Appearance
- Ability to taste food
- Ability to chew food
- Pain on mastication
- General satisfaction

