8.2 Intra-oral radiographs

Standardized intra-oral periapical radiographs will be obtained of each site when the implants are placed and uncovered, at final implant restoration and at twelve and twenty-four months after the implants are placed. A minimum of five radiographs per study site over the duration of the study will be obtained. Additional radiographs may be obtained based on the study dentist's determination of need.

Radiographs will be used to monitor osseous health at the bone-implant interface, to verify implant position, to assess the quality of implant-attachment interface and to capture measurements of longitudinal osseous support to the implants.

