12.1 Objective Data

Bone biopsies preserved in the trephines and stored in formalin will be submitted to UAB's CMBD (Name of facility) Core Laboratory. Trephine core 2x6mm will be stained with hematoxylin and eosin and processed for histologic and histomorphometric analysis. Amount of bone fill and remaining bone graft (% of new bone fill, % of residual graft and % of soft tissue) material will be determined and compared across groups.

Cone Beam Computed Technology (CBCT) will be used to capture quantitative natural bone fill and bone fill following grafting applications at each extraction site.

Image analysis software will be used to capture images from the standardized radiographs taken at 12 and 24 months following implant placement. Analysis procedures will assess the implant/bone interface and measure changes in adjacent crestal alveolar bone levels over time.

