12.3 Outcome Endpoints

The primary efficacy parameter for implant success will be the duration of implant survival from surgical placement to 24 months post-placement across all groups. Measurement of bone height along the implant mesial and distal surfaces at 12 and 24 month follow-up evaluations will be captured from radiographic images and compared to same measurements at insertion. These measurements will be used to derive changes from baseline values.

Efficacy endpoints will include implant and prosthesis function as assessed by gingival health, bone levels and participant subjective satisfaction with the study therapy. Differences between groups will be calculated and used to determine if osseous changes and implant function are different across extraction groups and between implant groups.

Safety will be evaluated by clinical signs and symptoms of dental and medical events.

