This SA will be addressed using a survival analysis approach. The primary outcome measure will be presence of signs and symptoms of infection at the implant site, since implant failure is expected to be rare to non-existent. Frequencies of occurrence of infection will be tabulated for each implant type.

Cox proportional hazards regression will be used to evaluate the rates of infection for LTT and RBT implants, allowing for adjustment for potential confounding variables and covariates. A blocking variable representing the individual subject will be included in order to reflect multiple implants per study subject.

SA-8: Assess peri-implant soft tissue healing adjacent to LTT and RBT surfaced implants

The JEMPT index will be evaluated at the time of final restoration and at 12 and 24 months follow-up evaluations. Mixed model ANOVA will be used to compare changes over time between implant types. The statistical test that will be of primary interest is the implant type by time interaction.

SA-9: Assess changes in the longitudinal crestal bone levels across extraction groups and between implant groups at 12 and 24 months after surgical placement.

The analysis for the SA will be mixed-model ANOVA, accounting for multiple observations per subject. The statistical test that will be of primary interest is the F-test for surface type by time interaction.

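### SA-8 and SA-9 name no term for arch, although the schedule gives mandibular and maxillary sites different time in function at the same visit, and the uncovering and restoration films enter no analysis

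*Combined protocol and SAP*

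**What the plan says.** Both arches are eligible (Section 3.1): maxillary anterior teeth, and premolars of either jaw. Section 6.1 sets the general timing of uncovering by arch: "mandibular implants will be uncovered and restoration initiated approximately 4 months after placement; maxillary implants will be uncovered and restoration initiated approximately 6 months". The decision itself rests on the investigator's judgement of integration. Section 6.2 then states: "Prosthetic restoration of the implants will require numerous visits to the restorative dentist over a period of one to two-months". Follow-up runs on a different clock. Under Section 7.1, "Participants will return to the clinic at 12 and 24 months following implant placement", whatever the arch.

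Section 8.2 schedules standardised periapical films "when the implants are placed and uncovered, at final implant restoration and at twelve and twenty-four months after the implants are placed", at least five per site. One of their listed uses is to measure bone support over time.

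Section 12.3 defines the bone endpoint from the 12- and 24-month measurements, which "will be captured from radiographic images and compared to same measurements at insertion". Section 12.1 says image analysis software will "capture images from the standardized radiographs taken at 12 and 24 months following implant placement".

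In Section 12.4, smoking is the only covariate named for all models, and Section 4.2 makes it the only stratification factor. SA-8 follows a soft-tissue index from final restoration to 12 and 24 months: "Mixed model ANOVA will be used to compare changes over time between implant types". SA-9 tests surface type by time for crestal bone. Neither names arch. Section 4.4 gives all of a patient's sites the same collar.

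**The concern.** The same visit label stands for different amounts of time in function in the two jaws. In SA-9, the change from insertion to month 12 combines months before the crown with months after it, in proportions that depend on arch. In SA-8, the first interval (restoration to month 12) has a different length in each arch.

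Arch is known from the treatment plan before randomisation, so it is an ordinary baseline covariate at site level. Without it, any arch-related spread in the outcome is left in the error terms, and a chance imbalance of arch between collars goes uncorrected. A patient may have up to four sites, possibly in both jaws. A random subject effect does not remove differences between arches within a patient.

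Interpretation of Hypothesis III is also at stake. Section 12.3 counts bone level among the indicators of implant and prosthesis function, and Section 1.8 anticipates that early-placed implants may lose crestal bone whatever their design. If loss common to both collars occurs before restoration, a single change from insertion cannot show it. The two intermediate films could.

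**Working it through.** **1. The plan's own power figure.** Section 12.5 gives 70% power at 0.50 SD and 80% power at 0.565 SD for the collar comparison, with an effective 50 per collar, two-sided at 5%. A two-sample t-test (noncentral t, 98 degrees of freedom) gives 69.7% and 0.566 SD. The figures reproduce.

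**2. Months since the final crown.** Formula: visit month − uncovering month − (1 to 2 months of restoration). Inputs are from Sections 6.1, 6.2 and 7.1.

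| | Placement to crown | Since crown, month 12 | Since crown, month 24 |
|---|---|---|---|
| Mandible | 4 + (1 to 2) = 5-6 | 12 − (5 to 6) = 6-7 | 24 − (5 to 6) = 18-19 |
| Maxilla | 6 + (1 to 2) = 7-8 | 12 − (7 to 8) = 4-5 | 24 − (7 to 8) = 16-17 |

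The gap is about 2 months at both visits; across the restoration range it runs from 6 − 5 = 1 to 7 − 4 = 3. In relative terms, the midpoints give 6.5/4.5 = 1.44 at month 12 and 18.5/16.5 = 1.12 at month 24.

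Of the insertion-to-12-month interval, 5/12 to 6/12 (42-50%) precedes the crown in the mandible and 7/12 to 8/12 (58-67%) in the maxilla.

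**3. Films.** Five are scheduled: placement, uncovering, restoration, 12 months and 24 months. Sections 12.1 and 12.3 together use placement, 12 and 24 months. Two of five have no stated role in any analysis.

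**4. Precision (assumed inputs).** The documents give neither the maxillary share p nor the arch difference g in mean bone change, measured in within-arch SDs. Take p = 50-80% and g = 0.2-1.0, and read the plan's SD as the within-arch SD. Omitting arch multiplies the SD by √(1 + p(1−p)g²).
- Smallest case, p = 0.8, g = 0.2: √(1 + 0.16 × 0.04) = 1.003; power at 0.50 SD is 69.4%; detectable difference at 80% power about 0.57 SD.
- Largest case, p = 0.5, g = 1.0: √(1 + 0.25 × 1) = 1.118; power 60.0%; detectable difference about 0.63 SD.

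**5. Chance imbalance (same assumptions).** With n = 40 to 50 independent units per collar, the 95% range of the difference in maxillary share is ±1.96 × √(2p(1−p)/n).
- n = 40, p = 0.5: ±0.219.
- n = 50, p = 0.8: ±0.157.

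At 2 months per site, that is ±0.31 to ±0.44 month of mean functional time between collars. In outcome units the shift is g times the imbalance: at g = 0.5, about 0.08 to 0.11 SD; at g = 1.0, about 0.16 to 0.22 SD.

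**The case against.** **Bias.** A reader might infer that unequal timing biases LTT against RBT. The documents do not support that. Collar is randomised by patient, so arch is balanced in expectation and type I error is not threatened. Any unstratified baseline factor can be imbalanced by chance.

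**The clock.** A reader might also infer that the placement clock is a slip, or that the last visit is presented as 24 months of function. Aim 9 in Section 2.3 asks expressly about 12 and 24 months after placement. The heading of Section 7.1, though it calls the visits post-restoration, states the same clock. Total change from placement is a legitimate estimand.

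**SA-8.** It starts at restoration, so it has no submerged phase to mix. The point about films concerns crestal bone only.

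**Films and covariates.** The extra films also serve to monitor bone health, verify position and check the attachment, so they are not wasted. Naming smoking for all models does not forbid other covariates. What remains is that no analysis gives these two films a role, and neither SA-8 nor SA-9 names arch.

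**Size.** The 44% gap belongs to month 12 and falls to 12% by month 24. The precision loss depends wholly on assumptions and is negligible at the lower end. A gain of 5-11% in effective sample, from 1/(1 − R²), needs arch to explain 5-10% of the variance. With a 50-80% maxillary share, that means an arch difference of about 0.46 to 0.83 SD, similar to or larger than the collar effect the trial is powered for. The documents give no evidence for or against that.

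**Time axis.** Replacing the time variable by months since restoration would be tempting but unsound for the main comparison. Uncovering depends on judged integration, which collar could affect, so that axis is set after randomisation.

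**Conclusion.** The point holds as an inexpensive improvement to the analysis, not as an error that invalidates it. By the plan's own figures, arches differ by about two months in time since the crown at each visit, and 5-6 (mandible) or 7-8 (maxilla) months of the first bone-change interval precede the crown. These months assume that the approximate uncovering times are met; actual spread may be wider.

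The effect on power ranges from almost nothing to roughly ten percentage points, and rests on assumed values of the maxillary share and the arch effect. The firmer ground is interpretation: as specified, SA-9 cannot separate bone change before restoration from change after it, although the films to do so are already scheduled.

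**What to change.** 1. In Section 12.4, keep change from placement to 12 and 24 months as the main SA-9 estimand. Add arch and arch-by-time as fixed effects in SA-8 and SA-9.
2. In Sections 12.1 and 12.3, provide for measuring the uncovering and restoration films. As a prespecified secondary, descriptive analysis, report bone change by collar for three consecutive intervals: insertion to uncovering, uncovering to restoration, and restoration to 24 months.
3. State two limits. The later intervals are bounded by events after randomisation, so they are not protected comparisons. An arch term also carries tooth type, because mandibular sites are premolars only, so it does not isolate time in function.

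No visit, film or clinical rule changes. The cost is SAP wording, reading two more films per site, and a few degrees of freedom: 1 + 1 = 2 in SA-9 with two follow-up times, and 1 + 2 = 3 in SA-8 with three. Keeping the interval analysis descriptive avoids adding formal collar tests to a comparison with 70% power.
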